Incisional hernia (IH) is a defect in the abdominal wall at the position of a surgical scar that leads to a protrusion of abdominal content through the defect. It is a common complication after midline laparotomy with incidences ranging from 9 % to 40 % in the general population (1-11) and up to 69 % in high-risk patients (5,12-14). Incisional hernias can cause chronic pain, reduced quality of life (QoL) (15), impaired abdominal wall function and there is a risk of bowel obstruction, incarceration and ischemia. IH are also a great cost to the society (16,17). Several studies on IH prevention have been performed. An established intervention to avoid IH is to add a synthetic mesh to the suture closure of the abdomen after midline laparotomy. Meta-analyses have shown that the use of a prophylactic mesh significantly reduces the rate of IH after laparotomy compared with suture alone (18-22). Reported IH rates after onlay mesh closure of midline laparotomies are listed in Table 1 and in table 2 the corresponding numbers 5 years postoperatively are shown. Onlay mesh increases the risk of seroma compared to suture (RR 2.21), but the rate of wound infections (RR 1.32) and hematomas (RR 1.19) are comparable (22). The suture technique also matters and slowly absorbable monofilament suture at a 4:1 ratio to the incision length and small (5 mm) suture bites and steps also seems to be important to reduce IH rate after laparotomy (23). The mesh intervention is not frequently used in Norway and there are no Norwegian studies on IH prevention after midline laparotomy. There are two ongoing multicenter studies studying prophylactic mesh versus small stitch suture technique; the Finish PREEMER study compares retro-rectus mesh position to suture (24) and the German HULC trial studies onlay mesh versus suture in elective laparotomies (25). Hopefully the results will guide us on when to use prophylactic meshes on Norwegian patients. This study is an effort to contribute to our common knowledge, as well as to inspire Norwegian surgeons to consider using prophylactic meshes.

Table 1 – studies on IH after onlay mesh placement

Author	Type of study	Elective or emergency	% IH with suture	% IH with onlay mesh	Follow up
Hassan MA et al (21)	Meta-analysis	Elective 5 Emergency 1 Combined 1	32 %	10 %	mean 27 m median 24 m
Ulutas ME et al (26)	RCT	Emergency	27 %	4 %	12 m
Argudo N et al (27)	Retrospective analysis	Emergency	33 %	6 %	Mean 17 m

Based on results from comparable studies listed in Table 1 (onlay mesh versus suture) we estimate an IH rate of 30 % in group A and 10% in group B. We add on 20% loss to follow up at 12 months follow up due to the nature and known mortality rate in the emergency patient population amounting to about 70% of the laparotomies performed at SIH in 2023. With an alpha = 0.05 and power of 80% the number of patients needed in the study groups are 62 + 12 in each group, in total about 150 patients. If the loss to follow up turns out to be higher than 20%, the number of included patients will be increased accordingly.

8) Time frame

We plan to start the study in the autumn of 2024 after study approval and after training the involved surgeons and OR nurses in both the small stitch suture technique and the mesh application technique. We estimate inclusion to be complete at the end of 2026 and follow up at the end of 2027. During the following 6 months data will be analysed and the study results submitted for publication at the end of 2028.

9) Inclusion criteria

Surgery predominantly done by midline laparotomy
Age \geq 18 years
Written consent by patient/family
Midline laparotomy with delayed closure
No exclusion criteria

10) Exclusion criteria

Age $<$ 18 years
Pregnancy
Previous abdominal midline hernia mesh repair
Abdominal compartment syndrome
Linea alba closure not possible
Hernia in the midline with transverse diameter $>$ 2 cm
Life expectancy $<$ 6 months

11) Description of consent

Patients will be asked to participate in the study at the outpatient clinic or during their stay at the ward before surgery. Written consent is mandatory to be included in the study. The participants can at any time withdraw their consent. The patient data will from then on not be used in future analysis. If the anonymous data at the time is already included in the analysis, the data will not be deleted.

Elective surgery

The patients who are included in an elective setting will in most cases be identified at the outpatient clinic by a surgeon. This is not necessarily the same surgeon who will perform the surgery on the operating day. The patient will give consent to a resident, a junior doctor or a nurse either at the outpatient clinic when the medical record is taken or when the patient arrives at the ward before surgery. By not involving the

operating surgeon in this matter, the pressure of participating in the study will be reduced.

In some cases, the planned procedure of laparoscopy will be converted to a midline laparotomy perioperatively. If there is a high risk of conversion preoperatively, the patient will be offered to participate in the study given that the surgery is converted to a laparotomy.

Emergency surgery

The risk of developing IH after an emergency surgery is increased (OR 4.7 CI 3.9-5.5) (30). The two studies published on onlay prophylactic synthetic mesh in emergency laparotomies show a reduction in IH in the mesh group (4% and 6%) compared to the group closed with suture alone (27,4% and 33%) (26,27). One study also shows a reduction in burst abdomen within the first 30 postoperative days (31). The current guidelines of European Hernia Society (EHS) and American Hernia Society (AHS) (32) make no recommendation regarding prophylactic mesh reinforcement in emergency laparotomy as “the data on mesh augmentation are heterogeneous and limited”. The guidelines states “More research is needed to draw definitive conclusions on potential benefits of mesh augmentation in patients undergoing emergency midline laparotomy and to identify subgroups of patients who might benefit from prophylactic mesh placement».

In our opinion it is critical to include emergency laparotomies in this study as this is the patient group where surgeons are most reluctant to implement prophylactic mesh even though these patients are probably benefiting the most from reinforcement. Some of these patients will not be able to be included in the study due to the urgency of the operation or the state of the patient. However, patients with Glasgow Coma Scale score 15 that can confirm why they need surgery and what the treatment plan is, will generally be eligible for study inclusion if there is time before surgery. As in an elective setting, the patient will give his consent to the resident, the junior doctor or the nurse on call and not to the operating surgeon, to reduce the patients perceived pressure to consent to the study.

12) End of study

The study will end when the desired numbers of participants have been included (150).

The study will be terminated if:

- The estimated inclusion timespan doubles from 1,5 years to more than 3 years.
- More than 30% of patients are lost to follow up during the first 12 months of the inclusion period significantly impacting on the estimated timeframe of the study.

- Interim analyses after 40 included patients in both study groups reveals that 20 patients or more have had to have the mesh removed.

13) Procedure description

Study group A: small stitch suture closure of linea alba

Closure of linea alba will be performed according to EHS guidelines (32): Slowly absorbable monofilament 0 suture (PDS plus 0) is used. The fascia is closed by running suture with minimum 4:1 suture: incision length ratio with small bites technique (stitches 5 mm apart, 5-9 mm stitch depth on both sides, see Figure 1). Self-locking knots are tied in both ends of the suture line. A subcutaneous drain is used at the discretion of the surgeon and the skin is closed with skin clips.

The subcutaneous drain will be removed according to standard postoperative treatment, typically when output is below 30-50 ml/24 hours, and skin clips 10-14 days postoperative in patients without signs of SSI. The OR nurse will together with the surgeon, measure used suture material and incision length on individual patients and the data will be written on a registration form for each patient.

[figure not shown]

Figure 1

Study group B: small stitch suture closure of linea alba + onlay polypropylene mesh
(Macroporous Polypropylene Mesh)

The same suture technique and suture material as described for study group A is used in study group B to close linea alba. The anterior rectus fascia is dissected 3 centimetres in all directions from the incision and a macroporous polypropylene mesh cut to fit this area is then applied (Figure 2), overlapping fascial edges by 3 cm in all directions as shown on Figure 2. The mesh used are cut from 15 cm x 15 cm meshes and if the incision is longer than 9 cm, more than one stripe is needed to cover the suture line, and the mesh stripes will overlap 3 cm. The mesh will be sutured to the fascia by interrupted PDS 2.0 stitches 3 cm apart around the circumference of the mesh. A subcutaneous drain is placed on top of the mesh before the skin is closed with skin clips. The drain will be removed after 2-5 days according to output below 30-50 ml/24 hours. Skin clips will be removed after 10-14 days in patients without signs of subcutaneous infections.

The OR nurse will together with the surgeons, measure used suture material and incision length on individual patients and the data will be written on a registration form for each patient.

[figure not shown]

Figure 2

14) Patient data

Demographic and clinical data that will be registered from electronic patients' charts are:

Age
Gender
Work/profession (physical or non-physical)
Medication (immunosuppression/steroids)
ASA
Diabetes Mellitus
Connective tissue disease
BMI
Smoking
Elective/Planned vs emergency surgery
Surgical procedure performed
Contamination classification (1-4)
Antibiotics (prophylactic/treatment, type?)
Surgery time
Length of stay (LOS)
Subcutaneous drain removed on day number
Intervention: Suture or Mesh
Suture length
Incision length
SL/WL
Burst abdomen
Sick leave
Discharge to home or home care facility
Clavien Dindo complication grade ≥ 3 during hospital stay
SSO intervention

15) Antibiotics

All patients receive prophylactic antibiotics or treatment according to procedure and status, typically Cefalotin 2g in vascular procedures and Doxycyklin 400 mg + Metronidazole 1g in GI procedures, alternatively Piperacillin Tazobactam treatment in contaminated and/or emergency patients with contaminated abdominal cavity.

16) Thromboprophylaxis

All patients receive anticoagulation treatment as decided by the surgeon. Typically, low molecular weight heparin (LMWH) after surgery for at least 10 days (4 weeks)

after cancer surgery). Vascular procedures are often followed by platelet inhibition after discharge.

17) “Open abdomen” / Delayed closure of the fascia

In the situations where the laparotomies cannot be closed primarily, the patients will be randomized initially at the time of the primary operation and then closed according to the assigned group at the final closure of the fascia.

18) Reoperation within the first 12 months

In the event of relaparotomy after initial closure within the first 12 months, the patient is further analysed as part of his original group (A and B) as in intention to treat manner. If a patient is reoperated due to burst abdomen, a mesh will likely be added for patients in group A (standard suture closure without mesh). These patients are also further analysed as a part of their original randomized group as in intention to treat manner.

19) Postoperative activity restrictions

All patients will have physiotherapist-guided mobilization after surgery focusing on unstrained (low abdominal pressure) mobilization for 8 weeks after surgery.

20) Evaluation/Follow up

Patients will be interviewed and examined 4-6 weeks and 12 months after surgery in the outpatient clinic. In cases where the patient cannot show up to a clinical examination, a telephone interview will be performed. Incisional hernia occurrence will be evaluated clinically and by CT examination after 12 months. A QoL (EQ-5D) score and VAS-score will be performed preoperatively in patients scheduled for elective surgery. This cannot be performed in emergent cases due to considerable bias implicated by acute illness and the need for surgery. QoL (EQ-5D) score will be calculated at the scheduled postoperative follow ups in all patients. Total length of sick leave will also be registered as well as average pain over the last 24-48 hours measured by VAS-score. Any sign of symptomatic SSO will be further explored by ultrasound or CT scan at 4-6 weeks follow up.

In the application for study approval by the regional ethics committee and the local data protection officer, we will apply for storage of data over time to perform longterm follow up as well (5 years follow up). In accordance, we will ask for written consent from the patients to contact them after one and five years postoperatively.

21) Data storage and statistics

Registration forms will be stored in coded lockers in the department. Extracted data from electronical medical charts (DIPS extracted data) will be entered with identification code into Excel and thereafter transferred for analyses into SPSS. We might use LEDIDI for data storage if this system becomes available during the study period. The identification code will be stored separately on a safe institutional server domain approved and provided by the hospital.

Descriptive data analyses will be performed.

Continuous data will be analysed by Mann-Whitney U test and multiple logistic regression.

Categorical data will be analysed by Chi-Square tests and multiple logistic regression.

Kaplan-Meier analyses for IH rate comparison will be conducted.

Interim analyses of group differences will be performed as Mann-Whitney U test or Chi-Square tests as appropriate.

22) Ethics

Study approval will be applied to the regional ethics committee and the local data protection officer.

All patients will receive standard care in abdominal wall closure, but group B patients will probably benefit from the additional mesh by a potential reduced risk of IH after surgery. The previous studies conducted on onlay prophylactic mesh (21,26-29) show a significant reduction in IH rate with the use of a prophylactic mesh. As data are not considered strong enough by the hernia society in Europe or USA to strongly recommend the use of prophylactic meshes (32), we cannot claim to deprive some patients of better outcome by not giving them a mesh prophylaxis.

In our experience most Norwegian surgeons are reluctant to apply prophylactic meshes as they are not familiar with the method and afraid of infections. It is our belief that if it were not for the participation of this study, most of the patients would not receive a prophylactic mesh as it is not the standard of care today. We hope that this study will contribute to increase the use of prophylactic mesh in midline laparotomies and create more awareness of the procedure to the general Norwegian surgeons.

Seroma and infections

As previous studies have shown that implementation of prophylactic onlay mesh increases the risk of seroma, some of the patients in study group B may receive an unnecessary complication. However, we believe that the benefit of reducing IH is greater than the possible risk for this non-serious complication that in most cases may be resolved either spontaneously or by bedside procedures.

The mesh is made of inert large pore material (polypropylene) that facilitates good vascular ingrowth which makes the resistance to infection good due to antibiotic penetration in vascularized tissue. The mesh can easily be removed with a surgical procedure in local or general anaesthesia. Fluid accumulation around the mesh (seroma) is probably prevented by adding a subcutaneous suction drain that are removed with a slight discomfort (with oral or iv pain medication) after a few days. In most cases the drains are removed without pain due to the epidural anaesthesia most of the patients have the first days after laparotomy.

Mesh infections are rare, and the incidence of mesh removal is low in published studies (21,26,27,29). The risk of a potential harmful procedure performed in general anaesthesia is therefore very small. By choosing onlay position of the mesh, the risk of organ injury in a reoperation is reduced and the layers used for potential later hernia repair preserved.

Excluded groups

We have chosen to exclude pregnant woman, children and patients who have previously gone through abdominal midline hernia mesh repair from the study. There are no studies conducted on pregnant women or children on this matter. Pregnant women and children have abdominal walls that are, respectively, expanding and a rupture or tear of the abdominal wall next to a fixed area (the edge of the mesh) is possible. The patients previously treated for abdominal midline hernia mesh repair need a different closing technique after laparotomy, and these patients are therefore not eligible for this study.

23) Funding

The added cost generated by the study is estimated to:

- about 15 minutes OR time (58)
- about 300 NOK in added materials (mesh + drain)
- outpatient clinic appointment at 12 months
- CT scan at 12 months
- SPSS, LEDIDI licenses or similar for 1-2 study group members

These costs are funded by the surgical department and signed for by the director of the surgical department, [name].

24) Contact

[name], [contact].
M [name]

[name] PhD, [contact].
M [name]

[name] PhD, [contact].
M [name]

25) Appendix

- Consent form
- Registration forms

26) References

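### Sample size (section 7): the 20% loss allowance is added as 20% of 62, so 150 enrolled leaves 60 evaluable per group instead of 62; 156 would be needed (minor)

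*Protocol*

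**What the plan says.** Protocol section 7 (Sample size) sets the planning assumptions: "we estimate an IH rate of 30 % in group A and 10% in group B", and "With an alpha = 0.05 and power of 80" per cent. On attrition it says "We add on 20% loss to follow up at 12 months follow up", and explains this by the mortality expected among emergency patients. The result is that "the number of patients needed in the study groups are 62 + 12 in each group, in total about 150 patients". A contingency follows: "If the loss to follow up turns out to be higher than 20%, the number of included patients will be increased accordingly".

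Section 12 (End of study) uses the same total to close enrolment: "The study will end when the desired numbers of participants have been included (150"). One of its termination criteria is "More than 30% of patients are lost to follow up during the first 12 months of the inclusion period", where this affects the time frame.

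Section 21 (Data storage and statistics) names the test: "Categorical data will be analysed by Chi-Square tests and multiple logistic regression".

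**The concern.** Section 7 uses one percentage on two different bases. The 12 extra patients are a fifth of the 62 who must be evaluable. The contingency sentence, however, treats 20% as the loss observed among those included. A loss rate acts on everyone enrolled, including the extra patients, so adding a fifth of 62 and then losing a fifth of the enlarged group does not return 62.

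The figure matters because it is also the number at which enrolment stops. At exactly the planned loss the trial falls short of its own evaluable target, and no rule in the protocol is triggered to correct it. The same method would leave a larger shortfall if it were repeated at a higher loss rate. Section 7 foresees higher loss, and section 12 sets a termination limit only above 30%.

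**Working it through.** **Inputs (section 7).** p_A = 0.30, p_B = 0.10, alpha = 0.05, power = 80%, equal groups, loss = 20%. The protocol does not state whether alpha is one- or two-sided. Two-sided reproduces its figure; one-sided would give 49 per group.

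**Step 1: reproduce the base.** Pooled two-proportion formula without continuity correction, with mean rate p = 0.20:

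n = [1.960·√(2·0.20·0.80) + 0.842·√(0.30·0.70 + 0.10·0.90)]² / (0.30 − 0.10)² = 61.6, so **62 per group**. This matches the protocol.

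**Step 2: reproduce the allowance.** 0.20 × 62 = 12.4, taken as 12. Then 62 + 12 = 74 per group and 148 in total, rounded to about 150. So the method was n × (1 + loss).

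**Step 3: the allowance that preserves 62.** The requirement is N × (1 − 0.20) = 62, so N = 62/0.80 = 77.5. That is **78 per group, 156 in total**: 3 per group, or 6 in total (6/156 = 3.8%), more than the stated 150.

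**Step 4: what the stated number delivers at 20% loss.**

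| Enrolled per group | Evaluable at 20% loss | Power, pooled formula |
|---|---|---|
| 74 (148 in total) | 59.2 | 78.4% |
| 75 (150 in total) | 60.0 | 78.9% |
| 78 (156 in total) | 62.4 | 80.5% |

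With exactly 62 evaluable per group the formula gives 80.3%.

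**Step 5: the loss that 150 can absorb.** 1 − 124/150 = 17.3% (16.2% if 74 per group is taken literally: 1 − 62/74). Between 17.3% and 20% loss the target is missed by up to 2 per group, and the contingency in section 7 does not yet apply.

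**Step 6: power of the named test.** Exact enumeration of the uncorrected two-sided chi-square test at 30% against 10% gives 80.2% at 60 per group and 81.0% at 62.

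**Step 7: if the top-up repeated the same addition.** This is an assumption; the protocol does not say how the increase would be computed.

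| Loss | By addition, per group | Evaluable | Power, pooled formula | 62/(1 − loss), per group |
|---|---|---|---|---|
| 25% | 62 × 1.25 = 77.5, so 78 | 78 × 0.75 = 58.5 | 77.9% | 82.7, so 83 |
| 30% | 62 × 1.30 = 80.6, so 81 | 81 × 0.70 = 56.7 | 76.6% | 88.6, so 89 |

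Exact chi-square power in the 30% row is between 78.1% (56 per group) and 78.9% (57 per group).

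**The case against.** The strongest reply is that nothing of practical importance is lost. With the uncorrected chi-square test, exact power at 60 per group is 80.2%, so the 80% target is met at the planned loss; only the pooled approximation falls below it. The unpooled formula also exceeds 80% at 60 per group (80.7%). The total is given as approximate, and 6 patients are few beside the uncertainty in the assumed rates: Table 1 shows 27% to 33% with suture and 4% to 10% with mesh, and the plan takes the least favourable of those mesh figures. All of this stands, and it is why the point is minor. It does not make 62 + 12 the right allowance for 20% loss.

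A second reply is that the unpooled formula needs 59 per group, and 59/0.80 rounds up to 74, the protocol's own figure. This is a coincidence: the protocol names 62 as the base and 12 as the addition.

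A third reply is that the top-up scenarios are conjecture, since the contingency sentence may well mean restoring the required number, and its formula could be left to a statistical analysis plan. That is fair. The scenarios show only what the existing method would do if it were reused; they are not an error in the text. The finding rests on the planned 20% alone.

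**Conclusion.** The concern holds, as a minor error. The enrolment figure in section 7, repeated in section 12, does not follow from the stated inputs: 150 against 156 enrolled, and 60 against 62 evaluable per group at 20% loss. The cost in power is about 1.4 percentage points by the pooled formula (80.3% − 78.9%) and 0.8 by exact calculation (81.0% − 80.2%). The design is not put at risk.

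This assumes a two-sided alpha, equal groups, loss equally spread over both groups, no continuity correction, and patients treated as individually randomised, as in the protocol's own calculation. With a continuity correction, power would be lower at both 60 and 62 per group; that is a separate matter.

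**What to change.** Restate the figure in section 7 in one of two ways:

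1. Keep 150 and say what it delivers: 60 evaluable per group at 20% loss, with about 79% power by the pooled formula (80.2% by exact calculation for the uncorrected chi-square test), and 62 per group preserved up to about 17% loss. This needs no extra patients.
2. Replace the sum by 62/0.80 = 78 per group, 156 in total, and change the 150 in section 12 to match. This needs 6 more patients.

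Under either option, state that any increase for higher loss is computed as 62/(1 − loss) per group: 83 at 25% loss, 89 at 30%. As a separate drafting point, section 12 could refer to the number in section 7 as increased, so that the fixed 150 does not conflict with the top-up.

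The cost is a sentence or two in section 7 and, under the second option, one number in section 12.

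### The protocol cites a strong effect of emergency surgery on incisional hernia and records it, but does not tie the primary comparison to it; naming it as the single adjustment factor would be a free improvement

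*Protocol*

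**What the plan says.** Five places in the protocol bear on this.

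- **Section 11 (Emergency surgery)** gives the prognostic effect: "The risk of developing IH after an emergency surgery is increased (OR 4.7 CI 3.9-5.5".
- **Section 7 (Sample size)** describes the case mix, an "emergency patient population amounting to about 70% of the laparotomies performed at SIH in 2023", and the planning rates: "we estimate an IH rate of 30 % in group A and 10% in group B". It then states "With an alpha = 0.05 and power of 80% the number of patients needed in the study groups are 62 + 12 in each group".
- **Section 14 (Patient data)** includes the item "Elective/Planned vs emergency surgery" in the list to be registered.
- **Section 6 (Study design)** has the technique drawn from closed envelopes each Monday for the whole week. It mentions no stratification by urgency of surgery.
- **Section 21 (Data storage and statistics)** says "Categorical data will be analysed by Chi-Square tests and multiple logistic regression" and adds Kaplan-Meier analyses for the hernia rate. It names no covariates and does not call any of these methods primary.

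**The concern.** On the protocol's own figures, the trial mixes two large groups of patients with very different hernia risk. When such a factor is known before closure and already recorded, an analysis that ignores it gives up a little precision. It also lets the result depend partly on how many emergencies happen to fall in each arm.

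Section 21 leaves crude, adjusted and time-to-event analyses all open for the same endpoint. If nothing settles the choice before the data are seen, it could be made after it is known which way the case mix fell.

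An unspecified logistic model is also a weak safeguard. With about 60 evaluable patients per group, 60 × 0.30 + 60 × 0.10 = 24 hernias are expected, which supports very few covariates. Some of the 25 items in Section 14 (length of stay, burst abdomen, drain removal day, surgical site intervention) arise after closure, so they should not be used to adjust the mesh effect.

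**Working it through.** **Inputs.** Rates of 30% and 10%, alpha 0.05, power 80%, and 62 per group (Section 7). Emergency share 70% (Section 7, one hospital in 2023; assumed to carry over to the trial). Odds ratio 4.7, interval 3.9 to 5.5 (Section 11; assumed common to both arms). About 150 patients less 20% loss leaves 75 × 0.8 = 60 per group, so both 60 and 62 are used. Individual randomisation is assumed throughout.

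**1. The plan's figure.** Two-sided, pooled variance, no continuity correction:
n = [1.96 × √(2 × 0.20 × 0.80) + 0.8416 × √(0.30 × 0.70 + 0.10 × 0.90)]² / 0.20² = (1.109 + 0.461)² / 0.04 = 61.6, so 62. The stated size reproduces, as an unadjusted two-proportion calculation.

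**2. Risks by stratum.** Solve 0.7 × p(emergency) + 0.3 × p(elective) = group rate, with odds ratio 4.7.

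| | Elective | Emergency |
|---|---|---|
| Group A (30%) | 11.5% | 37.9% |
| Group B (10%) | 3.1% | 13.0% |

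**3. Variance removed by stratifying.** Crude: 0.30 × 0.70 + 0.10 × 0.90 = 0.300. Within strata: 0.3 × (0.115 × 0.885 + 0.031 × 0.969) + 0.7 × (0.379 × 0.621 + 0.130 × 0.870) ≈ 0.283. The ratio is 0.944 with unrounded risks (0.954 to 0.936 over the odds ratio's interval). So 62 per group acts like 62 / 0.944 ≈ 66, and formula power goes from 80.3% to 82.5%.

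**4. Size of chance imbalance.** The SD of the difference in emergency share is √(2 × 0.7 × 0.3 / 60) = 8.4 points at 60 per group. A gap above 10 points in either direction has a probability of about 23%, so about 12% in each direction. At 62 per group the SD is 8.2 points, and 95% of differences lie within about 16 points. The mean risk gap between strata is (26.4 + 9.9) / 2 ≈ 18 points, so a 16-point imbalance shifts the crude risk difference by about 0.16 × 18 ≈ 2.9 points. The crude standard error is √(0.300 / 62) = 7.0 points, and the planned difference is 20 points.

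**5. Simulated power** (crude chi-square against Cochran-Mantel-Haenszel without continuity correction, 200,000 runs per line):

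| Situation | Crude | Stratified |
|---|---|---|
| 62 per group, averaged over chance imbalance | 81.0% | 83.1% |
| 60 per group, averaged | 80.2% | 81.8% |
| 60 per group, emergencies 65% in A, 75% in B | 73.1% | 82.0% |
| 60 per group, emergencies 75% in A, 65% in B | 87.0% | 81.5% |

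A repeat run agreed to within about 0.2 points.

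**6. Sensitivity.** At 60 per group with an odds ratio of 1.5 to 2, the two tests are within about 0.3 points of each other. With a continuity correction, the stratified test falls to about 74% to 76% power at an odds ratio of 4.7, below the crude test.

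**7. Type I error**, averaged over chance imbalance at 62 per group: close to 5% for both tests (crude 4.7% to 4.9%, stratified 4.8% to 5.2% across runs).

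**The case against.** A reader might infer that the protocol makes an unadjusted chi-square its primary comparison. It does not. Section 21 lists multiple logistic regression in the same sentence and Kaplan-Meier for the hernia rate, and ranks none of them. A sample size based on two proportions does not bind the analysis to a crude test. Choosing covariates is also ordinary content for a statistical analysis plan, and one may exist that is not shown. This objection stands, and it is why the point is a suggestion.

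Nor does the protocol say that every item in Section 14 will enter the logistic model. That section is a registration list, and it includes outcomes and the treatment itself. Overfitting is a risk of leaving the model open; it is not something the plan prescribes.

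Quoting only the drop to 73% would be one-sided. The opposite imbalance raises the crude test to 87%, above the stratified test, and the average gain is about 2 points.

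The odds ratio itself may not transfer. It is a single outside figure, and the 38% risk it implies for emergency suture closure exceeds both emergency suture rates cited in Section 11 (27.4% and 33%). The mostly elective meta-analysis in Table 1 reports 32% with suture, close to those emergency rates, although follow-up differs. With a weak effect the gain vanishes. However, stratifying then costs at most a few tenths of a point, provided no continuity correction is used.

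**Conclusion.** The point holds as an optional improvement. The protocol quantifies a strong predictor and records it, but uses it neither in the allocation nor in any stated commitment for the primary comparison.

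Under the assumptions above, adjusting for it gains about 2 points of power on average. More usefully, it keeps power near 82% when a 10-point imbalance would move the crude test between about 73% and 87%.

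Two stronger readings are not supported. The crude test is not invalid, since its type I error averaged over chance imbalance stays near 5%. The sample size is not wrong either: 62 per group follows from the stated inputs.

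Two assumptions could shift the size of the gain. Section 11 says that some emergency patients cannot be included. A lower emergency share would raise the gain slightly: at 50%, formula power at 62 per group is 83.8%, against 82.5% at 70%. Allocation by whole weeks was not modelled. If emergencies cluster by week, imbalance could be wider than shown here.

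**What to change.** Add to Section 21, or to the analysis plan before any outcome data are examined:

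- The primary analysis is incisional hernia at 12 months compared between groups, adjusted for elective/emergency status only. Use either a Cochran-Mantel-Haenszel test without continuity correction together with the Mantel-Haenszel risk difference, or logistic regression with group and elective/emergency as the only terms. Choose one of the two in advance.
- The crude chi-square is reported as supportive.
- No variable arising after closure is used as an adjuster, and any further covariates are limited to what about 24 events can carry.

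The cost is a sentence or two. The variable is already collected, the protocol's chosen software can run the analysis, and the sample size, allocation and patient care do not change. Check that the software's reported Mantel-Haenszel test is the uncorrected one, since the corrected form would lose power against the crude test.
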